8.2 Adverse event reporting

All adverse events will be reported to the study coordinator and recorded. The HREC procedures for reporting serious adverse incidents within 72 hours will be followed. Completing and submitting HREC adverse event templates and contacting the HREC office directly with urgent issues will be followed.

The data collection procedures are monitored to ensure the accuracy of the data. Data collection monitoring includes monitoring of the consistency of data analysis, quality of video recordings, and the timeframes for uploading videos to the data storage after each therapy or assessment session. The supervisors check the data collection procedures weekly for the students they supervise. Data collection procedures are discussed at supervision meetings and adjustments are implemented where required.

Page 18 of 21 The effectiveness of Rapid Syllable Transition Treatment in improving communication in children with cerebral palsy: A randomized controlled study

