6.6.3 Usual Care Group

Children randomised to the usual care control group will continue to receive their usual care therapy. Families will fill in a weekly online questionnaire that includes questions about i) the family's satisfaction with the child's speech, ii) use of the child's high technology AAC if the child has one, and iii) content and the dose of usual care therapy. Once the Treatment phase 1 Follow up assessment T3 has been completed, this group will begin ReST therapy. The families in the Usual first- group are asked to fill in this questionnaire weekly and emailed to the study coordinator, [name] while they are waiting to commence treatment.

Page 14 of 21 The effectiveness of Rapid Syllable Transition Treatment in improving communication in children with cerebral palsy: A randomized controlled study

The families will email the questionnaire to the study coordinator. If the families neglect to answer the questions, the study coordinator will contact the family and remind the family to email the questionnaire. If the family is unable to email the answers, the questionnaire will be conducted over the phone with the study coordinator or the speech pathology students.

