6.11 Protocol Violations

To minimise and prevent protocol violation, the following will occur: The written treatment protocol will include instructions on the delivery of ReST, data recording, and data storage.

Provision of adequate training of speech pathology students on the delivery of ReST. Regular and on-going supervision of the students and observation of their treatment sessions.

Procedure for recording treatment dosage and participant responses at each session. Procedure for recording participant behavior and engagement after each session. Procedure for logging all data recording and storing.

If a protocol violation occurs, the person responsible will inform the Principal Investigator (PI) or, in case of a student, their student supervisor within 24 hours. The PI or the student supervisor records the violation in the protocol violation form. A plan to rectify the violation will be decided between the person responsible for the violation, their supervisor where relevant, and the PI. This is also recorded in the protocol violation form.

6. 12 Participant reimbursement

There are no participant reimbursement or incentives.

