7.1.1 Potential Risks

This is a relatively low-risk project and does not pose foreseeable risks to the participants or their families. The speech pathology involvement is not different from the usual speech pathology practice but may involve mild distress from time to time as tasks may be difficult for the child.

As this is a trial study of ReST with children with CP, there is a risk of no improvement in speech intelligibility or communicative participation at the end of the study. The families are informed of this at recruitment.

Participants receive treatment from speech pathology students. There is a small risk that the students' inexperience may impact on the intervention quality or the ability to recognise subtle signs of participant fatigue, however previous ReST studies involved speech pathology students successfully in the treatment delivery, including McCabe, et. al (2014) and Murray, et. al. (2015) studies. Students will be supervised by the research team members and will receive guidance and support to maintain a high standard of service delivery and participant care.

Privacy and confidentiality pose a risk. This is covered in section 9 Data Management.

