8. SAFETY CONSIDERATIONS

8.1 Assessment and Documentation of Adverse Events

To ensure consistent procedures and safety of the participants, the participants' progress and will be monitored. Speech pathologists in the research team will supervise the speech pathology students who deliver the treatment. This includes monitoring the maintenance of accurate delivery of ReST treatment and to ensure the participants' experiences during the treatments are positive. The supervisor provides feedback and support during and after the treatment sessions. Adherence to the treatment protocol and participants' experiences are discussed and adjustments are implemented where required.

Children who become distressed will be provided with a break, with encouragement, and with appropriate support in consultation with them and their parents. If the child and the parent consent to continuing, the session will recommence after a short break. Otherwise, the session will be discontinued.

Direct observation of the students occurs during the first four sessions of the treatment block. After this, the frequency of direct observation is gradually reduced to once a week, in line with usual practice. As all sessions will be recorded, the student and the supervisor can review the sessions where the supervisor was not present.

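### Adverse events are actively looked for in ReST sessions but no equivalent is described for usual-care time, so recorded events would tend to over-represent ReST

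*Protocol*

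**What the plan says.** Section 8.2 sets the rule: "All adverse events will be reported to the study coordinator and recorded". It names a destination for reports. It does not say how events are to be elicited, and it is not restricted to one group or period.

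The means of detection are in other sections:

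- **Section 8.1**, which is headed for adverse event assessment: "Speech pathologists in the research team will supervise the speech pathology students who deliver the treatment". One stated purpose is "to ensure the participants' experiences during the treatments are positive". "Direct observation of the students occurs during the first four sessions of the treatment block", after which observation tapers to weekly, with recordings available for the rest.
- **Section 6.11**, in a list about ReST delivery: "Procedure for recording participant behavior and engagement after each session".
- **Section 6.6.3**, the weekly usual-care questionnaire: the family's satisfaction with the child's speech, then "ii) use of the child's high technology AAC if the child has one, and iii) content and the dose of usual care therapy". No harm topic is listed. Families who do not reply are reminded, and a phone call is the fallback.
- **Section 6.2**: in phase 2 the ReST-first group has the T4 and T5 assessments and nothing else.
- **Sections 7.2 and 9.1**: staff are told to watch for fatigue and frustration at assessments as well as in treatment, and assessments are videoed. Section 7.1.2 says both groups have all the assessments.

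Section 6.13 makes continuation of the trial depend on adverse or serious events not occurring. Section 7.1.1 describes the expected risk: "The speech pathology involvement is not different from the usual speech pathology practice but may involve mild distress from time to time".

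**The concern.** A count of adverse events reflects both how often they happen and how hard anyone looks. Under ReST, a student sees the child at every session, a supervisor watches some sessions, all are recorded, and a note on behaviour and engagement follows each one. In usual-care time nobody from the study sees the child between assessments, and the form that families return each week lists nothing about harm. If the plan is followed as written, equal true rates would tend to appear as more events under ReST.

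Three things are at stake. Section 8.2's promise to record all events is not backed by a method in the non-ReST periods. The events that inform continuation under 6.13 would come disproportionately from ReST time. An event in a non-ReST period may also come to light late, which fits poorly with the 72-hour reporting procedure that 8.2 adopts for serious incidents.

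**Working it through.** The protocol states no adverse event rate, detection figure or event comparison, so there is no figure of its own to reproduce. The check has two parts.

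**1. Scheduled contacts in phase 1, per child (section 6.2)**

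- ReST-first: 3 sessions a week × 6 weeks = 18 sessions; with T2 and T3, 18 + 2 = 20 contacts, all with study staff.
- Usual-care-first: T2 and T3 give 2 staff contacts. T3 falls three weeks after the final session, so the phase lasts about 6 + 3 = 9 weeks. Allowing 6 to 10 weekly questionnaires (an assumption), the total is 2 + 6 = 8 to 2 + 10 = 12 contacts, of which only 2 are in front of staff and none includes a listed harm question.

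For ReST-first children in phase 2, T4 is due within a week of the end of the second ReST block. If that block starts straight after T3, the interval with no described contact is about 6 to 7 weeks.

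**2. What unequal detection does to the record (illustration)**

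Let r be the true event rate and d the probability that an event is recorded, with equal time in each condition. Then

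ReST share of recorded events = r_R·d_R / (r_R·d_R + r_U·d_U).

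Assume d_R = 0.9 and let d_U vary. For equal rates and d_U = 0.30: 0.9 / (0.9 + 0.30) = 75%. For a ReST rate half the usual-care rate and d_U = 0.10: 0.45 / (0.45 + 0.10) = 82%.

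| True rate, ReST ÷ usual care | d_U = 0 | 0.05 | 0.10 | 0.30 | 0.50 | 0.90 (equal detection) |
|---|---|---|---|---|---|---|
| 0.25 | 100% | 82% | 69% | 43% | 31% | 20% |
| 0.5 | 100% | 90% | 82% | 60% | 47% | 33% |
| 1 | 100% | 95% | 90% | 75% | 64% | 50% |
| 2 | 100% | 97% | 95% | 86% | 78% | 67% |

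The last column is the true share. In every row the recorded share exceeds it whenever d_U is below d_R, so the direction of the bias is clear. Its size runs from nothing to total depending on d_U, which the protocol does not give. At equal true rates, a share of 90% needs detection nine times higher under ReST (0.9 ÷ 0.10).

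**The case against.** The case for leaving the text alone is substantial.

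- Section 8.2 is neutral between groups. Sections 7.2 and 9.1 extend observation to assessments that both groups attend. It is tempting to infer that events are sought only through ReST supervision; these sections rule that out.
- The questionnaire is described as including three topics, so the list may not be exhaustive, and the form is not shown. The supportable statement is that no harm item is listed.
- A reader might infer that nearly all recorded events must fall on ReST whatever the true rates, or that two affected children in each group of ten would yield two records on ReST and none on usual care. Either requires usual-care detection of exactly zero, which the protocol does not support.
- A reader might also infer that a serious event in a waiting child would stay unseen until the next assessment. Those families are in touch with the coordinator weekly. The gap is more plausible for ReST-first children between T3 and T4.
- No comparison of event rates is planned: safety is absent from the hypotheses (section 4), the outcomes (6.5) and the analysis (6.14). The sentence in 7.1.1 is a risk statement, not a claim that the trial sets out to test.
- Some of the imbalance would be real, since distress within a ReST session can arise only under ReST. Closer supervision of student-delivered treatment is also proportionate in a low-risk study.

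All of this limits the point without removing it. Watching a child at an assessment does not reveal what happened in the preceding weeks, and weekly contact helps only if harm is raised. How events are elicited is trial conduct and belongs in the protocol, whatever an analysis plan may add on reporting.

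**Conclusion.** The point holds in a limited form. Ascertainment differs between ReST and usual-care periods, and nothing described in the protocol equalises it. Recorded events would tend to over-represent ReST time, and events in non-ReST periods may be found late. The direction rests on one assumption, that an event is less likely to be recorded when nobody observes the child or asks about harm. The amount cannot be computed from the document, and the percentages above are illustrations under assumed detection. Because the trial crosses over and both groups receive ReST, the distortion lies between periods more than between groups of children. It does not touch the primary outcome or its analysis. This is a cheap improvement to safety recording, not a flaw that undermines the trial.

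**What to change.** 1. Add one fixed item to the weekly usual-care questionnaire in 6.6.3, for example: *Has your child had any distress, fatigue, frustration, or other health or therapy-related problem this week? If yes, please describe.*
2. Put the same item, worded for the session, in the after-session record in 6.11.
3. Ask it of every family in both groups at T2, T3, T4 and T5, covering the time since the last assessment.
4. State in 8.2 that events are reported by condition (ReST or usual care) and by phase, that some in-session distress can arise only under ReST, and that counts with 10 children per group are descriptive.

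If the common item is not added, say in 8.2 that event counts will not be compared between conditions.

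The cost is a slightly longer form and more minor events to log. The forms and visits already exist. One limit remains: for ReST-first children in phase 2, the item at T4 picks up events between T3 and T4 only in retrospect. Sending that group the weekly form as well would close the gap, at the price of an extra task for those families.

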9. DATA MANAGEMENT

9.1 Data collection and storage

Research data, including video recordings and assessment results are collected in electronic form. Identification codes replace names in all files.

All assessment and treatment sessions are videoed, which will then be uploaded by the treating student therapist to The University of Sydney approved Dropbox immediately after the session.

Paper copies of assessment forms are scanned and collected in electronic form.

Paper copies of intelligibility ratings are scanned and collected in electronic form.

The paper forms are shredded immediately after scanning.

The weekly online questions for the usual care group are collected weekly through REDCap survey and saved electronically.

Consent forms, contact details, and identifying codes will be held in a password protected encrypted file in the RDS.

Once the data is no longer being actively used it will be deleted from Dropbox and only retained in the RDS.

9.3 Data retention and archiving process

Data is stored for a minimum of 20 years or until subjects are 25 years following project completion. Since this is research about children, who once they become adults have legal rights for seven years (ie until they are 25), we may be required to be able to re-identify them if they choose to take up these rights. Only the investigators will have access to the code which could re-identify the child.

After this, the project materials will be permanently deleted from the RDS.

10. FINANCIAL

This study is not externally funded.

11. PUBLICATION POLICY / DISSEMINATION OF RESULTS

This work will be reported in one or more journal articles and conference papers. It will be included in [name]. Cerebral Palsy Alliance may report it in newsletters and the annual report or on their social media.

Authorship will follow the Contributor Roles Taxonomy (Credit). [name] will be 1st author, other authors will be determined by the nature and extent of their contributions to the papers.

15. APPENDICES

General comment: Always number the pages of your protocol and ensure the version date in the header or footer is correct and in a consistent format.
